• **Skeletal Muscle Biopsies:** Patients will lie comfortably in the supine position for biopsy of the vastus lateralis muscle of the non-dominant leg. Biopsy sites will be prepped with betadine. 2% xylocaine (without epinephrine) will then be administered, superficially initially and then more deeply into the muscle, using a small gauge needle. Subjects who have report a history of poor pain control or low threshold will be offered the use of a topical anesthetic cream prior to the xylocaine. Ultrasound may be used to enhance visualization of the site for the needle insertion. A small superficial incision will next be completed using a #11 blade scalpel. A 5 mm Bergstrom muscle biopsy needle will be inserted through the skin incision and advanced into the muscle. Suction will be generated using a syringe attached to the outside portion of the needle, to thereby suck skeletal muscle into a hole on the side of the needle positioned in the muscle tissue; this draws a small piece of muscle tissue (about 150 mg of muscle tissue) into the hollow shaft of the needle, which is then cut with a cutting trochar that slides through the shaft to cut the tissue drawn within its core. After harvesting the first sample, the needle will be rotated 90 degrees, and a second sample extracted to maximize yield for analysis. Additional passes of the needle may be necessary for an adequate muscle sample. The wound site will be closed with steri-strips and a sterile pressure bandage. Muscle specimens will be immediately processed, and stored. One fragment will be placed in sterile cryotubes containing RNA preservation solution (RNAlater) and immediately frozen in liquid nitrogen for measurement of mRNA expression. A second fragment will have the muscle fibers aligned for microscopy, placed in OCT, then cooled in a thawing isopentane slurry and placed in a cryotube and frozen in liquid nitrogen for morphological analysis. One specimen will immediately be used for high resolution respirometry. Briefly, muscle fibers will be dissected and immediately placed in an Oroboros respirometry. Basal respiratory rate will be measured followed by respiration after the administration of oligomycin A to assess non-productive respiration and FCCP to measure maximal respiratory capacity. A separate muscle specimen will be saved for Western blots and to measure nitrite concentrations by reductive chemiluminescence.

• **Transthoracic Echocardiogram.** The subject may be transported to UPMC Presbyterian for the echocardiogram.

• **24-hour Dietary recall.** The study coordinator will collect a second post 24-recall of all foods eaten the day before from subjects for analysis for calories, macronutrients, sodium, nitrates and nitrites.

End of Trial and Follow-Up Period

Post Study Drug Telephone Assessment (about 1 week following Visit 5)

• Telephone assessment for interval histories, muscle biopsy follow up and AEs.

Table 1. Study Assessment and Procedures

Visit	Screening	Baseline		Phone call follow-ups during intervention time				Final		FU
	1	2	3	1	2	3	4	4	5	Phone call
				1	2	3	4			1
Week of Treatment	-	-4~-1	-4~-1	1	2	3	4	5	5	6
Day of Treatment	-			7	~14	~21	~28	~25-35	V4+2-7d	
Time Window		V1+not >4 wks.	V2+ 2-7d	±2d	±7d	±7d	±7	±7d		About 1 week following V5
Visit Type	OP	OP	OP	Phone	Phone	Phone	Phone	OP	OP	Phone
Informed Consent / Eligibility Criteria	x									
History & Physical Exam	x									
Body Weight, Height (V1 only)	x	x	x					x	x	
Vital signs	x	x	x					x	x	
Methemoglobin %			x					x	x	
Research Labs			x						x	
Two Hour Safety Blood Sampling			x							
Two Hour HR, BP (sitting and after standing 3 mins.), Methemoglobin Monitoring: baseline & q15 min.			x							
Hemoglobin & hematocrit	x									
Echocardiogram	x								x	
Muscle Biopsy			x						x	
Physical Function Testing*		x						x		
Questionnaire-KCCQ or SF-12		x						x		
Meal/snack			x ^s						x ^s	
AE Assessment			x	x	x	x	x	x	x	x
Medication Compliance Review				x	x	x	x	x	x	
Interval History Assessment		x	x	x	x	x	x	x	x	X
Brief Physical Exam		x	x					x	x	
Symptom review			x	x	x	x	x	x	x	x
24 hour dietary recall		x	x					x	x	

^sStandard kitchen meal/snack

*includes nCPET, Steady State Walking, SPPB and Hand-grip strength

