2.2.5. Medication Compliance

Subjects will self-administer their first dose of study medication under the supervision of the CTRC nurse (physician investigator will be immediately available) in the outpatient CTRC during Visit 3, following completion of all baseline clinic assessments. Subjects will also be dispensed their study medication (42-day supply) for home use, including four 7-day prefilled and labelled pill boxes and drug/symptom diary cards to help with compliance and to help reduce burden or confusion. (Visit 4 may be scheduled up to and on the 42nd day from visit 3 (25-35±5 days); additional drug will be distributed with the initial dispensation if needed to meet the need.) Subjects will return the previously dispensed study medication when they return for Visit 4 approximately 4 weeks later (+1 week if need be for flexibility of scheduling) and medication compliance will be assessed. The study coordinator will review the daily diary card with each phone call evaluation and also assess medication compliance with queries regarding empty pill compartments in the current 7-day box and remaining boxes. In the event that the compliance rate is <80% (subjects' report of doses taken/total doses prescribed at that date & time *100), subjects will be re-educated on medication compliance. If medication compliance repeatedly falls outside of the acceptable range, the study investigators will discuss subject eligibility for continued participation in the study.

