This visit involves a percutaneous muscle biopsy, blood draw, first dose of study medication and dispensing of study medication. To prevent acute effects of exercise on muscle mitochondria function, this fasting visit will occur 2-7 days after Visit 2. This visit will take place at the MUH-CTRC and will last 4-5 hours. Subjects will be asked to observe 8 hours fasting prior to arrival. Upon arrival subjects will be weighed and then served a standardized breakfast [15% of 30 calories/kg current body weight (CBW) and 15% of 1.0 gm protein/kg CBW, low nitrite/nitrate] in

the CTRC. A dietitian will review and adjust subjects' food choices as needed to meet the standardized diet prescription.

Interval history and brief physical exam: temperature, blood pressure, pulse oximetry, breathing rate, heart rate and body weight. Blood pressures may be re-measured to allow for clinical variation. Prior to the biopsy, study staff will call indicated subjects to hold their anti-platelet and anti-coagulation medications for 1-5 days (depending on the different medications and relative half-lives). In each instance a subject is on an anti-platelet or anti-coagulation medication, the plan to hold the medication prior to the biopsy will first be cleared by the study physician with the subject's own primary care provider or cardiologist. Physician orders for CTRC will include confirmation with subject upon arrival.

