Subjects will rest for approximately 30 minutes post biopsy while wound is dressed and prior to baseline vitals prior to dosing. Study staff will record a baseline level of symptoms, including shortness of breath, dizziness, lightheadedness for use during weekly phone calls, prior to dosing.

Following biopsy, subjects will receive their first dose of study drug as follows:

- 14N sodium nitrite, 20 or 40 mg per physician order
- Blood pressure (sitting and then standing after 3 minutes), HR, RR, pulse oximeter and methemoglobin will be measured to ensure they are at a steady state before taking the study drug (baseline) and then approximately every 15 minutes for the 2 hours post-drug administration. Any perturbations of concern will be addressed per the Dose Reduction protocol described in Section 2.2.6.
- AE assessment
- Provide a 42-day supply of study drug, pre-filled in 4 weekly pill boxes and an extra bottle and drug diary cards to assist with compliance and reduce burden or confusion. Study staff will review medication administration and use of the drug diary card with all subjects. Study staff or CTCR RN will review biopsy site care with subjects and if indicated, remind subjects to resume their normal anti-coagulation and anti-platelet medications the following day (as indicated).
- 24-hour dietary recall. The study coordinator will collect a second 24-recall of all foods eaten from subjects for analysis for calories, macronutrients, sodium, nitrates and nitrites.

Subjects will be reminded before departure to report promptly any changes in their medication, health or symptoms of concern, not to wait for the weekly call.

Visit 4 (First Completion Assessment visit to be scheduled 25-35±7 days following first dosing of 20-40 mg oral nitrite) Subjects who need more than 42 days' supply of drug due to scheduling later in window will be issued additional at visit 3.

This visit will take place in the EMRC and/or Pepper SMART Center and is identical to visit 2 (approximately 3 hours):

Interval history and brief physical exam: temperature, blood pressure, pulse oximetry for methemoglobin %, breathing rate, heart rate and body weight; additionally, AE and symptom assessment will be collected and medication compliance via drug diary cards and pill boxes will be assessed.

Physical Function Battery:

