- Cardiopulmonary Stress Exercise Testing: Exercise testing in association with air-gas-exchange, an optimal gauge of aerobic capacity will be conducted by trained research exercise physiologists. [name] or another physician will be immediately available if needed. A computerized cycle ergometer using a ramp protocol will be used to generate a symptom limited exercise stimulus. A lightweight disposable pneumotach device face mask will be positioned over a subject's mouth and nose during the exercise for gas exchange assessments VO_2 , VE/VCO_2 slope, and respiratory exchange ratio (RER) will be measured as well as hemodynamics (max heart rate [HR] and blood pressure [BP]), time, and ECG waveforms). Any unexpected abnormalities will be reported to a patient's cardiologist or primary care physician; continued participation in the study will require physician clearance. Both the Borg Rate of Perceived Exertion (RPE) and the Modified Borg Scale for Perceived Dyspnea (Shortness of Breath) will be completed during the CPX. The EMRC has performed similar tests in more than 1,000 volunteers ranging from elderly women in their 80's to highly trained athletes.

- Short Physical Performance Battery (SPPB): a brief performance battery is used to assess how well older persons perform simple movements that represent the building blocks of daily activities that require good lower extremity function. It is based on a timed 4 meter walk, repeated chair stands, and a set of balance tests.
- Fatigability will be assessed based on rate of perceived exertion (RPE 6-20 scale) reported after a steady state walking on a treadmill. Patients will walk 1.5 miles/hour (0.67 m/sec) for 5 minutes on a treadmill as per techniques validated by Simonsick, et al. (J Am Geriatr Soc. 2014;62:347-51). Those with RPE ≥ 10 will be categorized as highly fatigued. Our prior work in HF patients indicates this steady state walking provocation is feasible for the patients we anticipate we will enroll, and that it will (appropriately) generate a wide range of perceived fatigability responses for meaningful analyses of underlying mechanisms.
- Hand Grip Strength Assessment will be performed to measure muscle strength. Participants will be asked to sit in a chair without arms and squeeze a device as hard as they can with one hand at a time, rest and switch to the other hand.

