- The Kansas City Cardiomyopathy Questionnaire will be used to measure disease-specific health-related quality of life (QOL). This 24-item instrument produces the following scores: Physical Limitation, Symptoms, Symptom Stability, Social Limitation, Self-efficacy, Quality of Life, and two summary measures, and is widely used as a standard by which quality of life, self-efficacy, and other personal perspectives related to functional capacity at baseline and over time. Subjects in the healthy elderly control group will be asked to complete the SF-12.
- 24-hour Dietary recall. The study coordinator will collect a post 24-hour recall of all foods eaten from subjects for analysis for calories, macronutrients, sodium, nitrates and nitrites.

Visit 5 (Final Completion Visit - 2-7 \pm 7 days following Visit 4)

Subjects will be fasting and take their last dose of study drug at home on their usual schedule prior to scheduled testing time. Upon arrival to the CTRC, subjects will be served a standardized breakfast as described in visit 3, then interval history and brief physical exam; temperature, blood pressure, pulse oximetry for methemoglobin %, breathing rate, heart rate and body weight will be documented; additionally, AE and symptom assessment, medication compliance via drug diary cards and pill boxes, and confirmation of last dose will be performed prior to assessment procedures. Prior to the biopsy, study staff will call indicated subjects to hold their anti-platelet and anti-coagulation medications for 1-5 days (depending on the different medications and relative half-lives). This visit will last approximately 2 hours.

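### The Visit 5 window sets no effective minimum gap between the Visit 4 exercise test and the final muscle biopsy, although the baseline biopsy has a 2-day minimum.

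*Combined protocol and SAP*

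**What the plan says.** **Baseline.** Section 2.3.1, Visit 3, fixes the gap and gives the reason: "To prevent acute effects of exercise on muscle mitochondria function, this fasting visit will occur 2-7 days after Visit 2". No tolerance is attached to it.

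**After treatment.** Section 2.3.1 says that Visit 4 "is identical to visit 2 (approximately 3 hours"). It includes the cardiopulmonary test: "A computerized cycle ergometer using a ramp protocol will be used to generate a symptom limited exercise stimulus". Visit 5 then takes a "biopsy of the vastus lateralis muscle of the non-dominant leg", the same site as at baseline, with one specimen going straight to respirometry and another kept for mRNA.

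**The Visit 5 window.** The heading opens "Visit 5 (Final Completion Visit - 2-7" and, after a plus-or-minus sign, ends "7 days following Visit 4". Table 1 lists Visit 5 as Visit 4 plus 2-7 days. As extracted, it shows no tolerance in the Visit 5 column.

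**Analysis.** Section 2.5 fits mixed models with group, time point and their interaction. Contrast (a) is the change over time within each group; contrast (b) compares those changes across groups. There is no term for time since exercise.

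**Study drug.** Section 2.2.5 states: "Subjects will return the previously dispensed study medication when they return for Visit 4 approximately 4 weeks later". The Visit 5 text has subjects take a last dose at home that day, which staff confirm.

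**The concern.** The protocol treats the 2-day minimum as a measurement safeguard. It applies the safeguard before the baseline biopsy and then, by adding a 7-day tolerance in both directions, drops it before the only post-treatment biopsy. A site that booked Visit 5 for the day after Visit 4 would be within the window, and no deviation would be recorded.

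All post-treatment muscle respirometry and gene-expression values come from that biopsy. All three groups receive nitrite and there is no untreated arm, so contrast (a) has nothing to subtract an exercise effect from. An acute effect in either direction, present after treatment but not at baseline, would be read as a nitrite effect or would mask one. In contrast (b) it would cancel only if it were equally frequent and equally large in each group.

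**Working it through.** **1. Length of the gap.** Inputs are the Visit 5 heading and the Visit 3 text in section 2.3.1.

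| Source | Earliest | Latest |
|---|---|---|
| Visit 2 to Visit 3 | 2 days | 7 days |
| Visit 4 to Visit 5, heading, literal | 2 - 7 = -5 days | 7 + 7 = 14 days |
| Visit 4 to Visit 5, heading, not before Visit 4 | 0 days | 14 days |
| Visit 4 to Visit 5, Table 1 as extracted | 2 days | 7 days |

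Day 0 is unlikely in practice. Visit 5 is a fasting visit with its own "second post 24-recall of all foods eaten the day before". Day 1 is feasible and nothing excludes it.

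**2. Number per group.** The plan states 30 subjects in three groups, so 10 per group is an inference. It can be checked against section 2.5, which gives detectable differences of 32 (within group) and 42 (between groups) for platelet respiration, with SD of change 32, 80% power and two-sided alpha 0.05. With n = 10 and the noncentral t distribution:

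- within group: 31.9, and power at 32 is 80.3%;
- between groups: 42.4, and power at 42 is 79.3%.

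Both match the plan, so 10 per group is a fair working figure. The point made here does not alter the sample size.

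**3. Bias in a group's mean change.** If k of 10 subjects are biopsied too soon and the acute effect is delta (in SDs of the change), then

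bias = (k / 10) x delta.

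The documents give no delta; 0.5-1.0 SD is assumed for illustration.

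**4. Effect on the 5% test.** Simulation: 400,000 runs, no nitrite effect, a one-sample t test on 10 changes, k of them shifted by delta. This approximates contrast (a); the planned mixed model pools variance over groups.

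| k of 10 | Bias (SD) | Rejection, delta 0.5 | Rejection, delta 1.0 |
|---|---|---|---|
| 1 | 0.05-0.10 | 5.0% | 5.0% |
| 2 | 0.10-0.20 | 5.5% | 6.6% |
| 3 | 0.15-0.30 | 6.4% | 9.8% |
| 5 | 0.25-0.50 | 9.9% | 21.7% |

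**5. How many might be affected.** The documents do not say. If visits fell evenly over days 1-14, 10 x 1/14 = 0.7 of 10 would be on day 1. Over days 0-14, 10 x 2/15 = 1.3 of 10 would be on day 0 or 1. Either figure is close to the first row of the table.

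**6. Drug supply.** The latest Visit 4 is day 35 + 7 = 42. The latest Visit 5 is then day 42 + 7 = 49 by Table 1, or 42 + 14 = 56 by the heading. The default supply is 42 days, with extra issued at Visit 3 if needed.

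**The case against.** **The literal window is not a credible instruction.** It starts five days before Visit 4, and staff know from the Visit 3 text why the gap exists. Evenly spread visits would put fewer than one subject in ten on day 1, and with one in ten the test keeps its level. This is a pilot that openly prefers a false finding to a missed one. All of this stands as an argument about size. It does not restore the minimum, and a preference for sensitivity does not help when the same effect could also hide a benefit.

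**A reader might infer that the heading contradicts Table 1.** The documents do not establish this. The table was machine-read, and it puts day ranges and tolerances in separate rows. The plus-or-minus 7 days under Visit 4 may originally have covered both final visits. If so, heading and table agree, and both conflict with the reason given at Visit 3.

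**A reader might infer from section 2.2.5 that subjects reach Visit 5 off drug, and that Aim 2 is lost.** The documents do not support either step.

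- The sentence on returning drug ends with compliance being assessed, which points to a count.
- The Visit 5 text calls for a home dose, confirmation of it and a check of pill boxes. Table 1 marks compliance review at both final visits.
- A 42-day supply already reaches the latest Visit 4, so provision for more than 42 days has a use only if dosing continues beyond it.
- Aim 2 also has plasma samples before and about 30 minutes and 2 hours after the first dose at Visit 3.

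What remains is that section 2.2.5 does not say the drug goes home again.

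**Conclusion.** The point holds for the biopsy gap and should be fixed. The Visit 5 heading allows a biopsy one day after symptom-limited exercise, against a 2-day minimum at baseline that the protocol itself justifies. That leaves the within-group pre/post change in muscle outcomes open to an exercise effect present only after treatment.

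The expected size is small: 0.05-0.20 SD of bias with one or two of ten subjects affected. It becomes material only if next-day visits are common. These figures rest on an assumed effect of 0.5-1.0 SD, 10 subjects per group and no nitrite effect. The case for acting rests on the stated safeguard and the low cost of restoring it, not on a demonstrated large bias.

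The drug-return wording is a minor clarification, and no off-drug consequence is claimed.

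**What to change.** **Main change.** In the Visit 5 heading, state that Visit 5 takes place at least 2 days after Visit 4, with a target of 2-7 days and tolerance on the late side only. Make the Visit 5 entry in Table 1 say the same. The cost is one line in two places and some lost scheduling flexibility, since a next-day Visit 5 is no longer allowed.

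**For any subjects already seen.** Days from exercise to biopsy can be derived from the visit dates. Listing them beside the muscle results would show whether anyone fell below 2 days.

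**Minor clarification.** In section 2.2.5, say that subjects bring the drug to Visit 4 for a count, keep it, and hand it in at Visit 5. State there and under Visit 4 in section 2.3.1 that the supply, including the existing extra-supply provision, covers dosing through Visit 5. The cost is a sentence in each place and a few more capsules for subjects scheduled late.

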2.2 DETAILED DESCRIPTION OF STUDY DESIGN

Subjects will undergo a screening visit to determine that eligibility requirements are met. Prior to receiving the study drug, subjects will be scheduled within 4 weeks of screening for a baseline assessment.

Subjects who meet the Inclusion Criteria and none of the Exclusion Criteria will be provided study drug. The study population ($n=30$) will receive oral sodium nitrite combination for 4 weeks:

Drug: oral formulation of sodium nitrite 20 or 40 mg oral three times daily or TID (once in the morning and again in the early afternoon and again in the evening)

Subjects will complete a 4-week outpatient treatment period. During the treatment period, subjects will be evaluated at weekly intervals. Throughout the study period, subjects will be asked to remain diligent in recording the time of study drug dosing and any associated symptoms (diary cards will be pre-dated).

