Chronic dietary supplementation of inorganic sodium nitrate in obese, hypertensive, insulin resistant mice lacking the gene for endothelial NO synthase (eNOS) (20) was studied. With a 10 week treatment of a modest dose of sodium nitrate of 0.1 mmol/kg/day (8.5 mg/kg/day) in the drinking water, significant reductions in blood pressure, fasting blood glucose, HbA1C, and proinsulin to insulin ratio were demonstrated, indicating reduced demands on the β -cell for insulin secretion.

Sodium nitrate drug is considered a source of nitrite through salivary nitrate reduction. Despite the plasma nitrite rise following a single oral sodium nitrate dose, Drs. [name], [name] and [name] recently demonstrated in a phase I PK/PD study in 10 normal volunteers that no persistent blood pressure reduction with sodium nitrate 1,000 mg. In contrast, in the same phase I PK/PD study in

10 normal volunteers, they showed blood pressure decline in systolic, diastolic and mean arterial pressures over 3 hours with sodium nitrite 20 mg. The oral sodium nitrite half-life was about 40-minutes and the effects of nitrite only lasted ≤ 6 hours. This was demonstrated by the plasma nitrite levels returning to baseline levels between 3 and 6 hours after nitrite dosing (i.e. the drug was given and gone out of the circulation within 6 hours). Specifically, mean baseline (pre-nitrite dosing) blood nitrite concentrations were 0.129 micromolar with a peak at 30 minutes of 5.5 micromolar, and return to baseline levels between the 3- (0.176 micromolar) and 6-hour (0.103 micromolar) monitoring time points. In addition, there were no serious adverse events when these normotensive individuals received sodium nitrite.

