- Blood sampling via IV line to include: research blood for inflammatory peptides (IL-1, IL-6, IL-15, TNF α), platelet sample and nitrite levels. Blood samples will be drawn into a 1) heparinized syringe (baseline and approximately 30 mins. and 2 hours post study drug administration) and 2) a cell preparation tube (CPT) (baseline and approximately 30 mins and 2 hours post study drug administration). Heparinized blood will be immediately centrifuged at bedside to separate plasma and the plasma and red cells separately flash frozen for later nitrite measurements (via reductive chemiluminescence to determine that nitrite levels were increased in the muscle as described. The second tube of blood (CPT tube) will be immediately subjected to differential centrifugation in order to isolate platelets. Platelets will then be subjected to Seahorse extracellular flux analysis in order to measure bioenergetic profile including basal, non-ATP producing, maximal and non-mitochondrial respiratory rates along with glycolytic rate. Extra aliquots will be stored for use in future studies. Two 10 ml purple top and 2 10 ml red top tubes will be used to collect blood for inflammatory peptides. Total volume of blood drawn will be 88 ml (6 tablespoons).

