- Blood draw to include: research blood for inflammatory peptides (IL-1, IL-6, IL-15, TNF α), platelet sample and nitrite levels: Two blood samples will be drawn into a 1) heparinized syringe and 2) a cell preparation tube (CPT). Heparinized blood will be immediately centrifuged at bedside to separate plasma and the plasma and red cells separately flash frozen for later nitrite measurements (via reductive chemiluminescence to determine that nitrite levels were increased in the muscle as described). The second tube of blood (CPT tube) will be immediately subjected to differential centrifugation in order to isolate platelets. Platelets will then be subjected to Seahorse extracellular flux analysis in order to measure bioenergetic profile including basal, non-ATP producing, maximal and non-mitochondrial respiratory rates along with glycolytic rate. Extra aliquots will be stored for use in future studies. Total volume of blood drawn will be 56 ml (4 tablespoons)

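### The single Visit 5 nitrite and platelet draw has no stated interval from the last home dose, so the 4-week plasma nitrite value carries avoidable timing variation.

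*Combined protocol and SAP*

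**What the plan says.** **Visit 5 (Section 2.3.1).** Subjects arrive fasting, having been told to "take their last dose of study drug at home on their usual schedule prior to scheduled testing time". On arrival they are served a standardized breakfast, and history and a brief examination follow. Before procedures, "medication compliance via drug diary cards and pill boxes, and confirmation of last dose will be performed prior to assessment procedures". The blood draw is the first procedure listed: "Two blood samples will be drawn into a 1) heparinized syringe and 2) a cell preparation tube (CPT". The syringe sample is for nitrite and the tube is for platelet bioenergetics. Neither the visit text nor Table 1 states how long after the dose the draw is made. The visit is said to last about 2 hours.

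**Visit 3 (Section 2.3.1).** The same two kinds of sample are timed: "baseline and approximately 30 mins. and 2 hours post study drug administration".

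**Dose times (Section 2.2).** During treatment, "subjects will be asked to remain diligent in recording the time of study drug dosing and any associated symptoms".

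**Kinetics (Section 2.2.2).** In 10 normal volunteers given 20 mg, "The oral sodium nitrite half-life was about 40-minutes". Mean nitrite rose from 0.129 micromolar before dosing to 5.5 at 30 minutes, with a "return to baseline levels between the 3- (0.176 micromolar) and 6-hour (0.103 micromolar) monitoring time points".

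**Use of the data.** Aim 2 is to show that plasma nitrite rises. Aim 3 relates that rise to muscle and platelet metabolism. Section 2.4 lists plasma nitrite as an endpoint, but Section 2.5 does not name it among the dependent variables. Section 2.5 models baseline against 4 weeks and does not say how the timed Visit 3 post-dose samples are used.

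**The concern.** A marker that falls this fast is hard to interpret without the time since dose. Two fully adherent subjects can give very different Visit 5 values because one lives further from the clinic or takes the morning dose earlier. A late draw can look like no increase.

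Three uses of the data are exposed:

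- the 4-week evidence for Aim 2;
- Aim 3, where plasma nitrite is the explanatory variable and timing noise in it can dilute an association with any measure that does not itself follow the current level;
- the nitrite descriptive statistics, if they are carried into sizing the next trial as Section 2.5 intends.

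The Visit 3 schedule shows that the authors recognised the importance of timing. The gap is at the 4-week assessment only.

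**Working it through.** **Inputs.** All are from Section 2.2.2: baseline 0.129, 30-minute mean 5.5, 3-hour mean 0.176 and 6-hour mean 0.103 micromolar; half-life about 40 minutes.

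**Step 1: check the protocol's own statement that levels return to baseline.**
- Peak rise: 5.5 − 0.129 = 5.371.
- Rise left at 3 h: 0.176 − 0.129 = 0.047, and 0.047 / 5.371 = 0.9%.
- Relative to baseline: 0.176 / 0.129 = 1.36 at 3 h, and 0.103 / 0.129 = 0.80 at 6 h.

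The statement holds. By 3 hours almost all of the rise has gone.

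**Step 2: level by time since dose.** Assume exponential decline above baseline from the 30-minute mean, with the stated half-life and t in minutes:

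C(t) = 0.129 + 5.371 × 2^(−(t − 30)/40)

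| Time after dose | C(t), micromolar |
|---|---|
| 1 h | 3.32 |
| 1.5 h | 2.03 |
| 1 h 45 min | 1.59 |
| 2 h | 1.26 |
| 2 h 15 min | 1.00 |
| 2.5 h | 0.80 |
| 3 h | 0.53 |

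**Step 3: variation from timing alone.** The documents do not give actual delays, so each window is illustrative. The SD is that of ln C(t) with delays spread evenly over the window.

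| Window | Ratio of the two ends | SD of ln nitrite |
|---|---|---|
| 1 to 3 h | 3.32 / 0.53 ≈ 6.3 | 0.53 |
| 1.5 to 2.5 h | 2.03 / 0.80 ≈ 2.5 | 0.27 |
| 2 h ± 15 min | 1.59 / 1.00 ≈ 1.6 | 0.135 |

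Going from a 1-hour spread (1.5 to 2.5 h) to a half-hour spread about halves the timing SD (0.27 to 0.135).

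**Step 4: limit of the model.** At 3 hours it gives 0.53, above the observed mean of 0.176. The baseline-corrected 30-minute and 3-hour means imply a half-life of 150 / log2(5.371 / 0.047) ≈ 22 minutes. That figure is imprecise because it rests on an excess of 0.047 micromolar. It would make the ratios larger: 12.6, 3.7 and 1.95. The conclusion uses the stated 40 minutes.

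**The case against.** **The delay is partly bounded.** This stands. Visit 5 lasts about 2 hours in all, the draw is listed first, and a fasting arrival with breakfast suggests a morning visit. The open part is therefore mainly the time from home dose to arrival, and the 1 to 3 hour spread is a wide case.

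**Silence does not prove that the draw time goes unrecorded.** This also stands. A laboratory or case report form outside the documents could capture it, and the diary covers the dose end. What can be said is that the protocol sets no interval and does not ask for the draw time.

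**A reader might infer that Visit 5 is off drug.** Section 2.2.5 says "Subjects will return the previously dispensed study medication when they return for Visit 4 approximately 4 weeks later" and mentions no re-issue, while Visit 5 follows nominally 2 to 7 days later. The documents as a whole do not support that reading. The Visit 5 text has an explicit home dose and a confirmation of it, and Table 1 schedules a compliance review at Visit 5. The 42-day supply reaches the nominal latest Visit 5 (day 35 + 7 = 42), with extra drug available at Visit 3. The return at Visit 4 may mean no more than bringing the boxes in for a count. It is a wording conflict to reconcile.

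**A reader might put a figure on the loss of correlation in Aim 3.** The documents do not support one. The correlations specified in Section 2.5 relate changes in skeletal physiology to strength, gait speed and balance; none involves nitrite. Such a figure would also need an assumed between-subject SD, and would need timing to be pure noise. If platelet respiration follows current nitrite, varied timing is partly real variation in exposure.

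**Conclusion.** The point holds and should be fixed. As written, the plan gives a noisier 4-week nitrite value than it needs to. With the stated half-life, timing alone contributes an SD of ln nitrite of about 0.27 if delays span 1.5 to 2.5 hours and 0.53 if they span 1 to 3 hours, against about 0.135 within 15 minutes of 2 hours.

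These sizes assume exponential decline, evenly spread delays, and kinetics in older subjects on 20 or 40 mg that resemble those of 10 normal volunteers on 20 mg. The missing interval itself needs none of these assumptions.

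The consequence is limited. The Visit 5 evidence for Aim 2 and the role of nitrite as explanatory variable in Aim 3 are weakened, but the timed Visit 3 samples still address Aim 2. The effect on platelet respiration cannot be sized from the documents. A reader might go further and infer bias between the three groups, or harm to the exercise test, walk or muscle outcomes. Nothing in the documents shows either.

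**What to change.** 1. Without changing dosing, schedule the Visit 5 draw in one stated window after the subject's usual-schedule dose, near a Visit 3 post-dose sampling time where feasible (about 2 hours).
2. Record clock times of the last dose and of the draw.
3. In Section 2.5, name log plasma nitrite as an outcome, say that the timed Visit 3 samples are used for Aim 2, and treat Visit 5 as the 4-week value.
4. Plot Visit 5 nitrite against time since dose as a descriptive display. Time since dose is undefined at the pre-drug baseline, so it should not enter the main baseline/4-week model.
5. State that the two visits are not fully comparable even at the same interval: the Visit 3 dose follows breakfast and biopsy, whereas the Visit 5 dose is taken fasting.
6. Reconcile the wording of Section 2.2.5 on return of medication at Visit 4 with the home dose before Visit 5.

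The cost is tighter Visit 5 scheduling, possibly some waiting time, a few time fields and a few lines of text. No extra subjects, blood draws or biopsies are needed.
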